10.2 Sylatron

SYLATRON, peginterferon alfa-2b, is a covalent conjugate of recombinant alfa-2b interferon with monomethoxy polyethylene glycol (PEG). The average molecular weight of the PEG portion of the molecule is 12,000 daltons. The average molecular weight of the SYLATRON molecule is approximately 31,000 daltons. The specific activity of pegylated interferon alfa-2b is approximately 0.7×10^8 international units/mg protein.

Interferon alfa-2b is a protein with a molecular weight of 19,271 daltons produced by recombinant DNA techniques. It is obtained from the bacterial fermentation of a strain of *Escherichia coli* bearing a genetically engineered plasmid containing an interferon gene from human leukocytes.

Each vial contains 200 mcg of peginterferon alfa-2b as a sterile, white to off-white lyophilized powder, and dibasic sodium phosphate anhydrous (1.11 mg), monobasic sodium phosphate dihydrate (1.11 mg), polysorbate 80 (0.074 mg), and sucrose (59.2 mg).

10.2.1 Supplier/How Supplied

Merck will supply sylatron at no charge to subjects participating in this clinical trial, as summarized in the table below.

Product Name & Potency	Dosage Form
Sylatron	Lyophilized Powder for Injection

10.2.2 Preparation

Reconstitute SYLATRON with 0.7 mL of Sterile Water for Injection, USP.

SYLATRON Single-Use Vial		Diluent (Sterile Water for Injection, USP)		Deliverable Product and Volume	Final Concentration
200 mcg*	add	0.7 mL	=	200 mcg in 0.5 mL	40 mcg/0.1 mL

Swirl gently to dissolve the lyophilized powder. **DO NOT SHAKE.**

- Visually inspect the solution for particulate matter and discoloration prior to administration. Discard if solution is discolored, cloudy, or if particulates are present.
- Do not withdraw more than 0.5 mL of reconstituted solution from each vial.
- Administer SYLATRON subcutaneously. Rotate injection sites.
- If reconstituted solution is not used immediately, store at 2°-8°C (36°-46°F) for no more than 24 hours. Discard reconstituted solution after 24 hours. **DO NOT FREEZE.**
- For single-use only. **DISCARD ANY UNUSED PORTION.**

10.2.3 Storage and Stability

SYLATRON should be stored at 25°C (77°F); excursions permitted to 15°-30°C (59-86°F) [see USP Controlled Room Temperature]. **DO NOT FREEZE.**

10.2.4 Handling and Disposal

Upon completion or termination of the study, all unused and/or partially used investigational product will be destroyed at the site per institutional policy. It is the Investigator's responsibility to arrange for disposal of all empty containers, provided that procedures for proper disposal have been established according to applicable federal, state, local and institutional guidelines and procedures, and provided that appropriate records of disposal are kept.

10.2.5 Dispensing, Returns and Reconciliation

The investigator is responsible for keeping accurate records of the clinical supplies received from Merck or designee, the amount dispensed to and returned by the subjects and the amount remaining at the conclusion of the trial.

10.2.6 Use in Pregnancy and Nursing Women

There are no adequate and well-controlled studies of SYLATRON in pregnant women. Nonpegylated interferon alfa-2b was an abortifacient in *Macaca mulatta* (rhesus monkeys) at 15 and 30 million international units (IU)/kg (estimated human equivalent of 5 and 10 million IU/kg, based on body surface area adjustment for a 60-kg adult). The estimated Intron A human

equivalent dose of 5 to 10 million IU/kg daily is approximately equal to a human equivalent dose of 79 to 158 mcg/kg/week of SYLATRON. Use SYLATRON during pregnancy only if the potential benefit justifies the potential risk to the fetus.

It is not known whether the components of SYLATRON are excreted in human milk. Studies in mice have shown that mouse interferons are excreted in breast milk. Because of the potential for adverse reactions from the drug in nursing infants, a decision must be made whether to discontinue nursing or discontinue the SYLATRON treatment, taking into account the importance of the therapy to the mother.

10.2.7 Adverse Events

Please refer to the current prescribing information for sylvatron for additional details. Most common adverse reactions (>60%) are: fatigue, increased ALT, increased AST, pyrexia, headache, anorexia, myalgia, nausea, chills, and injection site reaction. (6.1)

11 ADVERSE EVENTS

The descriptions and grading scales found in the NCI CTCAE v4 will be utilized for AE assessment. A copy of the CTCAE v4 can be downloaded from the CTEP website at <http://ctep.cancer.gov>. All forms for AE/SAE recording and reporting can be found in the Study Procedure Manual or in the EDC system (Documents and Information Tab).

11.1 Definitions

11.1.1 Adverse Event (AE)

An AE is any untoward medical occurrence whether or not considered related to the study drug that appears to change in intensity during the course of the study. The following are examples of AEs:

- Unintended or unfavorable sign or symptom
- A disease temporally associated with participation in the protocol
- An intercurrent illness or injury that impairs the well-being of the subject

Abnormal laboratory values or diagnostic test results constitute AEs only if they induce clinical signs or symptoms or require treatment or further diagnostic tests

Hospitalization for elective surgery or routine clinical procedures that are not the result of an AE (e.g., surgical insertion of central line) should not be recorded as an AE.

Disease progression should not be recorded as an AE, unless it is attributable to the study regimen by the site investigator.

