1.4.3.1 The safety of combining pembrolizumab and Sylatron

The safety of combining pembrolizumab and Sylatron has been evaluated in a phase I study. This safety and dose-seeking study of combination pembrolizumab and Sylatron for patients (≥ 18) with recurrent inoperable AJCC stage III and metastatic stage IV melanoma. Pembrolizumab is given 2 mg/kg q3 weeks for 2 years while Sylatron is given SC at 3 dose levels (1, 2 and 3 mcg/kg) to identify the recommended phase 2 dose (RP2D) prior to dose expansion up to 32 patients. Results: Twelve patients have been enrolled in this trial (4 patients at each dose level). No dose limiting toxicity has been observed to date. Most common side adverse events were grade 1 liver toxicities (n = 4), grade 1 neutropenia (n = 4), grade 1 skin rash (n = 3) and grade 1 anemia (n = 2). The only grade 3/4 toxicities were lymphopenia (n = 2) and hyponatremia (n = 1). Six out of 12 patients were evaluated for clinical responses at week 12 and we observed 1CR, 4SD and 1PD with mixed clinical responses (NCT02112032)[27]. In this current phase II study, the dosage of pembrolizumab and Sylatron are selected based on the data from the phase I study. Pembrolizumab will be administered at 200mg q 3 weeks, which is close to the dosage of pembrolizumab at 3mg/kg for a patient of 70 kg; Sylatron will be administered at 200mcg weekly, which is close to the dose of Sylatron at 3mcg/kg for a patient of 70 kg.

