2.2.2 Secondary Endpoints

- PFS defined as measurement from the date of registration until the criteria for disease progression is met as defined by RECIST 1.1 or death occurs. Subjects who have not progressed will be right-censored at the date of the last disease evaluation.
- OS is defined as the time of registration until death as a result of any cause.
- Objective response rate is defined as the sum of complete response (CR) + confirmed partial response (PR) and will be determined as per irRECIST.
- Grade 3 and 4 toxicities as defined by the NCI Common Terminology Criteria for Adverse Events (NCI CTCAE) v4.

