6.2 Dose Modification of Sylatron

Table 4: Dose Modification Guidelines of Sylatron for Drug-Related Adverse Events

Resume treatment at reduced dose (see Table 5)	Withhold treatment	Permanently discontinue treatment
Absolute Neutrophil Count (ANC) $\geq 0.5 \times 10^9/L$	Absolute Neutrophil Count (ANC) $< 0.5 \times 10^9/L$	Persistent or worsening severe neuropsychiatric disorders toxicity
Platelet Count (PLT) $\geq 50 \times 10^9/L$	Platelet Count (PLT) $< 50 \times 10^9/L$	New or worsening retinopathy
Non-hematologic toxicity has completely resolved or improved to Grade 1	Non-hematologic toxicity Grade ≥ 3	Grade 4 non-hematologic toxicity
ECOG PS 0-1	ECOG PS ≥ 2	Inability to tolerate a dose of 60mcg/week

Table 5: Sylatron Dose Modifications

Dose level -1	120 mcg weekly
Dose level -2	60 mcg weekly

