12.2.2 Definition of Secondary Endpoints

- PFS: defined as time from registration till the patient's disease progression or death from any cause whichever occurs first (those for whom event of progression or death not observed will be censored).
- OS: defined as time from registration till the patient's death from any cause (patient who are still alive at the end of the study will be censored).

- Objective response rate: defined as the proportion of subjects who achieve the best response (CR and PR) determined by irRECIST.
- Safety and tolerability of the combination of Sylatron and pembrolizumab as assessed by CTCAE v4. Will include patients' toxicity profile, adverse event, serious adverse event, serious adverse even leading to discontinuation of the treatment, death.

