12.4.2 Analysis Plans for Secondary Objectives

Progression free survival (PFS) and overall survival (OS) will be evaluated using the methods of Kaplan and Meier (1958). 95% confidence interval will be constructed for the estimated median PFS and OS. The exploratory objective response rate will be estimated with its 95% exact confidence interval. Safety summaries will be presented by the severity of the adverse event and by relationship to study drug. Descriptive statistics (minimum, maximum, mean median, standard deviation for continuous variables; counts, percentages for categorical variables) will be used in summarizing of all laboratory and safety parameters (adverse events, serious adverse events, adverse events leading to discontinuation, deaths) for all treated subjects.

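### A Grade 3-4 laboratory value without symptoms, treatment or further tests is not an AE, so the Grade 3-4 toxicity endpoint may undercount such events

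*Combined protocol and SAP*

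**What the plan says.** **Recording rule.** Section 11.1.1 says that abnormal laboratory or diagnostic results "constitute AEs only if they induce clinical signs or symptoms or require treatment or further diagnostic tests". No CTCAE grade overrides this rule.

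**Endpoint.** Section 2.2.2 lists "Grade 3 and 4 toxicities as defined by the NCI Common Terminology Criteria for Adverse Events (NCI CTCAE) v4" as a secondary endpoint. Section 12.2.2 describes safety as "toxicity profile, adverse event, serious adverse event, serious adverse even leading to discontinuation of the treatment, death" and does not say which records the toxicity profile comes from.

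**Grading and analysis.** Section 11 states: "The descriptions and grading scales found in the NCI CTCAE v4 will be utilized for AE assessment". Section 12.4.2 presents safety by AE severity and by relationship to treatment. It also applies descriptive statistics to "summarizing of all laboratory and safety parameters (adverse events, serious adverse events, adverse events leading to discontinuation, deaths) for all treated subjects". No laboratory table by CTCAE grade is named.

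**Dose holds.** Section 6 has subjects evaluated for AEs that lead to interruption of study drug. Table 4, whose title refers to drug-related adverse events, has neutrophil and platelet thresholds in its "Withhold treatment" column.

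**Prior data.** Section 1.4.3.1 reports on 12 patients given this combination in phase I: "The only grade 3/4 toxicities were lymphopenia (n = 2) and hyponatremia (n = 1").

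**The concern.** The endpoint is defined by grade. The rule that decides whether a laboratory finding is recorded as an AE is defined by symptoms, treatment or further tests. These are different criteria, and a value can meet the first without meeting the second. If Grade 3-4 toxicity is counted from AE records, which is the only severity tabulation the plan names, such a value is not counted.

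This matters more here than in most trials because all three Grade 3/4 events reported for the combination in phase I were laboratory findings. An undercount would make the combination look better tolerated than it is, on an endpoint that serves a stated secondary objective.

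**Working it through.** The plan gives no figure for this point, so there is nothing to reproduce. The check compares the passages and then gives an illustrative size.

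**Step 1. Apply the rule to the kinds of laboratory event the protocol mentions.**

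| Grade 3-4 finding | Route to being an AE under 11.1.1 | Exposed to loss? |
|---|---|---|
| Immune-related AST/ALT or bilirubin rise | Table 3 lists corticosteroids and repeat liver tests | Little |
| Combined AST/ALT, bilirubin and alkaline phosphatase pattern | Reportable under Section 11.6 whatever the symptoms | No |
| Hyponatremia | Falls under Table 4's hold for Grade 3 or higher non-hematologic toxicity; a hold alone is not a trigger in 11.1.1, but treatment or further tests would be | Possibly |
| Low neutrophils or platelets, managed only by a hold | None in 11.1.1 itself; Section 6 and Table 4 imply it is an AE | Depends on which section a site follows |
| Lymphopenia, no symptoms, not treated, not investigated | None; no row of its own in Table 3 or Table 4 | Yes |

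Table 3's row for other immune-related AEs does not rescue the last case, because it applies to events already judged to be AEs.

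**Step 2. Look for another route to the count.** Section 12.4.2 allows counts and percentages for categorical variables, and these apply to laboratory parameters too. A count by grade would fit that wording, but the plan does not specify one or link it to the endpoint in 2.2.2.

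**Step 3. Illustrative size.** Inputs: 12 phase I patients and 3 Grade 3/4 events (Section 1.4.3.1); 44 patients planned (Section 12.3). The text does not say whether one patient had both findings. Assumption: each lymphopenia is a separate patient, and the hyponatremia is either one of those two or a third, giving 2 or 3 patients.

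- Lower: 44 × 2/12 = 7.3, about 7 patients; 7/44 = 15.9% (exact 95% interval 6.6 to 30.1%). This is also the figure for lymphopenia alone.
- Upper: 44 × 3/12 = 11 patients; 11/44 = 25.0% (13.2 to 40.3%).

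**Step 4. What would be counted from AE records.** The share of these events meeting the AE rule is not in the documents, so the whole range is shown.

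| Share meeting the AE rule | Counted, if 7 true | Counted, if 11 true |
|---|---|---|
| All | 7 (15.9%) | 11 (25.0%) |
| Half (rounded) | 4 (9.1%) | 6 (13.6%) |
| None | 0 (0%; upper limit 8.0%) | 0 (0%; upper limit 8.0%) |

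The phase I rates are imprecise: the exact 95% interval is 2.1 to 48.4% for 2/12 and 5.5 to 57.2% for 3/12.

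**The case against.** A reader might infer that every asymptomatic Grade 3-4 laboratory value falls out of the endpoint. The documents do not support that, for four reasons.

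1. The rule joins its conditions with an *or*. An asymptomatic value that is treated or investigated further remains an AE, as many liver-test elevations would.
2. The endpoint is worded as toxicities, not AEs, and 12.2.2 lists the toxicity profile separately from adverse events. Nothing says it is derived only from AE records.
3. The laboratory summary in 12.4.2 is not confined to means and ranges.
4. Section 6 and Table 4 treat values that lead to a hold as adverse events. Resuming after a low neutrophil or platelet count presupposes a repeat count, which a site could regard as a further test.

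The projection is also weak: it carries three events in 12 melanoma patients, spread over three dose levels, to a different disease.

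All of this stands, and it limits the point to a possible undercount. It does not remove the point. No section assigns graded laboratory data to the endpoint, 11.1.1 has no grade or dose-hold trigger, and whether a repeat count is a further test is left undefined, so sites may record differently. Lymphopenia, the most frequent Grade 3/4 event in phase I, is reached by none of the specific protections except the general wording of 12.4.2.

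**Conclusion.** The point holds in a limited form. Followed as written, 11.1.1 keeps a Grade 3-4 laboratory value off the AE record when it causes no symptoms and requires neither treatment nor further tests. The plan names no other graded source for the Grade 3-4 toxicity endpoint. Such events may be missed, and any error from this source lowers the reported rate. Separately, 11.1.1 is out of step with Section 6 and Table 4 on values that lead to a dose hold.

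On the phase I rate, 7 to 11 of 44 patients could have a Grade 3-4 laboratory toxicity, with a loss anywhere from none to all of them. This assumes that the phase I rate carries over and that the endpoint is counted from AE records. It would be tempting to say that the severe-toxicity rate is biased downward. The documents show only that it can be, because neither the data source nor the share failing the rule is stated.

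The primary endpoint, sample size, alpha and power are not affected.

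**What to change.** **Section 12.4.2.** State that the Grade 3-4 toxicity endpoint combines AE records with the worst CTCAE v4 grade per patient derived from laboratory values, each patient counted once. Specify a table of worst on-treatment grade by laboratory parameter, shown against baseline grade, since Table 1 sets no entry limit for lymphocytes or sodium. Derived grades carry no investigator attribution, so report them regardless of relationship to study drug. Absolute lymphocyte count and sodium are already in the Section 7 laboratory list, and blood count and chemistry are scheduled on Day 1 of each cycle, at end of treatment and at safety follow-up.

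**Section 11.1.1.** Reconcile the recording rule with Section 6 and Table 4, so that a laboratory value that leads to withholding or reduction of study drug is recorded as an AE. This concerns recording only; it changes no dosing rule.

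**Cost.** Some programming on existing data, a few more AE entries at sites, and a somewhat higher reported toxicity rate. No new tests or visits are needed. Derived grades will still miss low values that fall between scheduled draws.

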11.1.2 Serious Adverse Event (SAE)

A SAE is an adverse event that:

- Results in death. **NOTE:** Death due to disease progression should not be reported as a SAE, unless it is attributable by the site investigator to the study drug(s)
- Is life-threatening (defined as an event in which the subject was at risk of death at the time of the event; it does not refer to an event which hypothetically might have caused death if it were more severe)
- Requires inpatient hospitalization for > 24 hours or prolongation of existing hospitalization. **NOTE:** Hospitalization for anticipated or protocol specified procedures such as administration of chemotherapy, central line insertion, metastasis interventional therapy, resection of primary tumor, or elective surgery, will not be considered serious adverse events.
- Results in persistent or significant disability/incapacity
- Is a congenital anomaly or birth defect
- Is an important medical event (defined as a medical event(s) that may not be immediately life-threatening or result in death or hospitalization but, based upon appropriate medical and scientific judgment, may jeopardize the subject or may require intervention (e.g., medical, surgical) to prevent one of the other serious outcomes listed in the definition above). Examples of such events include, but are not limited to, intensive treatment in an emergency room or at home for allergic bronchospasm; blood dyscrasias or convulsions not resulting in hospitalization; or the development of drug dependency or drug abuse.

11.1.3 Unexpected Adverse Event

For this study, an AE is considered unexpected when it varies in nature, intensity or frequency from information provided in the current IB, prescribing information or when it is not included in the informed consent document as a potential risk. Unexpected also refers to AEs that are mentioned in the IB as occurring with a class of drugs or are anticipated from the pharmacological properties of the drug, but are not specifically mentioned as occurring with the particular drug under investigation.

11.1.4 Relatedness

AEs will be categorized according to the likelihood that they are related to the study drug(s). Specifically, they will be categorized using the following terms:

Unrelated	Adverse Event is not related to the study drug(s)
Unlikely	Adverse Event is doubtfully related to the study drug(s)
Possible	Adverse Event may be related to the study drug(s)
Probable	Adverse Event is likely related to the study drug(s)
Definite	Adverse Event is clearly related to the study drug(s)

11.2 Reporting

11.2.1 Adverse Events

- AEs will be recorded from time of signed informed consent until 30 days after discontinuation of study drug(s).
- AEs will be recorded regardless of whether or not they are considered related to the study drug(s).
- All AEs will be recorded in the subject's medical record and on the appropriate study specific eCRF form within the EDC system.
- AEs considered related to study drug(s) will be followed until resolution to \leq Grade 1 or baseline, deemed clinically insignificant, and/or until a new anti-cancer treatment starts, whichever occurs first.

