6.1 Dose Delay of Pembrolizumab

Adverse events (both non-serious and serious) associated with pembrolizumab exposure may represent an immunologic etiology. These adverse events may occur shortly after the first dose or several months after the last dose of treatment. Pembrolizumab must be withheld for drug-related toxicities and severe or life-threatening AEs as per Table 3.

Table 3: Dose Modification and Toxicity Guidelines of pembrolizumab for Immune-related AEs Associated with Pembrolizumab

General instructions:				

 1. Corticosteroid taper should be initiated upon AE improving to Grade 1 or less and continue to taper over at least 4 weeks. 2. For situations where pembrolizumab has been withheld, pembrolizumab can be resumed after AE has been reduced to Grade 1 or 0 and corticosteroid has been tapered. Pembrolizumab should be permanently discontinued if AE does not resolve within 12 weeks of last dose or corticosteroids cannot be reduced to ≤ 10 mg prednisone or equivalent per day within 12 weeks. 3. For severe and life-threatening irAEs, IV corticosteroid should be initiated first followed by oral steroid. Other immunosuppressive treatment should be initiated if irAEs cannot be controlled by corticosteroids. 				
Immune-related AEs	Toxicity grade or conditions (CTCAEv4.0)	Action taken to pembrolizumab	irAE management with corticosteroid and/or other therapies	Monitor and follow-up
Pneumonitis	Grade 2	Withhold	
 • Administer corticosteroids (initial dose of 1-2 mg/kg prednisone or equivalent) followed by taper 	
 • Monitor participants for signs and symptoms of pneumonitis • Evaluate participants with suspected pneumonitis with radiographic imaging and initiate corticosteroid treatment • Add prophylactic antibiotics for opportunistic infections
	Grade 3 or 4, or recurrent Grade 2	Permanently discontinue		

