6.3 Subject Withdrawal/Protocol Therapy Discontinuation

Subjects may withdraw consent at any time for any reason or be dropped from the trial at the discretion of the site investigator should any untoward effect occur. In addition, a subject may be withdrawn by the site investigator or the sponsor-investigator if enrollment into the trial is inappropriate, the trial plan is violated, or for administrative and/or other safety reasons.

A subject must be discontinued from the trial for any of the following reasons:

- The subject or legal representative (such as a parent or legal guardian) withdraws consent.
- Confirmed radiographic disease progression
NOTE: A subject may be granted an exception to continue on treatment with confirmed radiographic progression if there is objective clinical benefit, please see Section 5.3
- Unacceptable adverse experienced
- Intercurrent illness that prevents further administration of treatment
- Site investigator's decision to withdraw the subject
- The subject has a confirmed positive serum pregnancy test
- Noncompliance with trial treatment or procedure requirements
- The subject is lost to follow-up
- Protocol therapy interrupted for > 12 weeks
- Completed 24 months of uninterrupted treatment with pembrolizumab or 35 administrations of pembrolizumab, whichever is later. **NOTE:** 24 months of pembrolizumab is calculated from the date of first dose.
- Administrative reasons

The End of Treatment and Follow-up visit procedures are listed in Section 7. After the end of treatment, each subject will have follow up visit (1) at 30 days after last dose of study treatment. Serious adverse events will be collected for 90 days after last dose of study treatment (follow up visit 2). Follow up for patients that have not experienced progression will occur every 9 weeks \pm 7 days. This may be done by phone call or other avenues as appropriate. Every effort should be made to obtain information on radiology scans or other types of disease assessment documentation. Once a subject experiences confirmed disease progression or starts a new anti-cancer therapy, the subject moves into the survival follow-up phase and should be contacted by telephone every 12 weeks \pm 7 days to assess for survival status until death, withdrawal of consent, or the end of the study, whichever occurs first.

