7. STUDY CALENDAR & EVALUATIONS

Study Evaluation Cycle = 21 days	Screening	On Treatment Cycle 1-n	End of Treatment Visit ¹¹	Safety Follow Up Visit ¹²	Long Term Follow Up ¹³
	≤ 28 days	Day 1 ± 5 days	± 7 days	30 days after EOT/study drug ± 7 days	Every 12 weeks after Visit 2
REQUIRED ASSESSMENTS					
Informed Consent	X				
Medical History ¹	X				
Diagnosis and Staging ¹	X				
Physical Exam ²	X	X ¹⁰	X	X	
Vital signs and ECOG Performance Status ³	X	X	X	X	
Baseline ophthalmologic assessment ⁴	X				
AEs & concomitant medications	X	X	X	X	
LABORATORY ASSESSMENTS					
Complete Blood Cell Count with diff (CBC)	X	X ¹⁰	X	X	
Comprehensive Metabolic Profile (CMP) and amylase	X	X ¹⁰	X	X	
PT/INR and aPTT	X	X ¹⁰	X	X	
Thyroid Function (TSH, free T4, T3)	X	X ¹⁰	X	X	
Urinalysis	X	X ¹⁰	X	X	
Pregnancy test (serum or urine) (WOCBP) ⁵	X				
DISEASE ASSESSMENT					
CT of chest ⁶	X	X			X
CT or MRI of abdomen and pelvis ⁶	X	X			X
MRI Brain ⁶	X	X			X
TREATMENT EXPOSURE					
Sylatron ⁷		X			
Pembrolizumab ⁷		X			
SPECIMEN COLLECTION					
Archival and Newly Obtained Tumor Tissue ⁸	X	X ⁸			
Blood Samples ⁹	X	X	X ⁹	X ⁹	
FOLLOW-UP					
Survival Status, Subsequent Therapy					X

Key to Footnotes

¹ During the medical history other information to be collected includes smoking history, alcohol history, diagnosis and staging and how the healthcare provider and/or subject learned about this study. Diagnosis and staging to include: reviewing pathology report and screening scans. Special attention should be given to the assessment of past or current depression or suicidal tendencies. In addition, if a subject has substance abuse issues, they are at higher risk of relapse. If concerns are identified during this visit, the appropriate referral to psychiatric services should be made to further assess. See SPM for additional information.

² Patients will be screened for depression, suicidal tendencies and possible relapse of substance abuse at each physical exam. If a concern is noted, the patient will be referred for the appropriate mental health evaluation. In addition, cardiac issues will be assessed per SOC and if concerns are identified, appropriate testing should be completed to fully assess the subject. This may include an EKG, ECHO/MUGA or cardiology referral.

³ Vital signs to include blood pressure, weight, and height (screening only) and ECOG performance status

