11.2.2 Serious Adverse Events (SAEs)

11.2.2.1 Site Requirements for Reporting SAEs to HCRN

- SAEs will be reported from time of signed informed consent until 90 days after discontinuation of study drug(s).
- SAEs will be reported on the SAE Submission Form **within 1 business day** of discovery of the event.
- SAEs include events related and unrelated to the study drug(s).
- All SAEs will be recorded in the subject's medical record and on the appropriate study specific eCRF form within the EDC system.
- All SAEs regardless of relation to study drug will be followed until resolution to \leq Grade 1 or baseline and/or deemed clinically insignificant and/or until a new anti-cancer treatment starts, whichever occurs first.

The site will submit the completed SAE Submission Form to HCRN **within 1 business day** of discovery of the event. The form may be submitted to HCRN electronically to [contact]. The site investigator is responsible for informing the IRB and/or other local regulatory bodies as per local requirements.

The original copy of the SAE Submission Form and the email correspondence must be kept within the study file at the study site.

Once the SAE has resolved (see resolution guidelines listed in 11.2.2.1), sites must submit a follow-up SAE Submission Form within a reasonable timeframe to HCRN electronically to [contact].

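### New non-serious Grade 3 immune-related events after day 30 are not recorded, although the protocol says they may occur months later and the Grade 3-4 endpoint has no stated window

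*Combined protocol and SAP*

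**What the plan says.** On timing of risk, Section 6.1 speaks of both serious and non-serious events linked to pembrolizumab, possibly of immune origin, and continues: "These adverse events may occur shortly after the first dose or several months after the last dose of treatment".

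On collection, Section 11.2.1 sets the limit for adverse events in general: "AEs will be recorded from time of signed informed consent until 30 days after discontinuation of study drug(s". For serious events Section 11.2.2.1 has "SAEs will be reported from time of signed informed consent until 90 days after discontinuation of study drug(s", and Section 6.3 agrees: "Serious adverse events will be collected for 90 days after last dose of study treatment (follow up visit 2". In the Section 7 calendar, the row "AEs & concomitant medications" is marked from screening through the 30-day safety visit and is blank under long-term follow-up. Section 5.5.1 matches this: beyond 30 days, concomitant medication is recorded only for serious events and events of clinical interest.

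On the endpoint, Section 2.2.2 lists "Grade 3 and 4 toxicities as defined by the NCI Common Terminology Criteria for Adverse Events (NCI CTCAE) v4". Section 12.2.2 restates safety as including "toxicity profile, adverse event, serious adverse event", among other items. Section 12.4.2 plans descriptive summaries by severity and relationship. None of the three gives a time window.

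**The concern.** The endpoint is wider than the data collected for it. It covers all Grade 3 and 4 toxicity, while after day 30 the plan looks only for serious events and two narrowly defined events of clinical interest. The shortfall falls in a period that the protocol itself names as one of risk for pembrolizumab, whose immune-mediated harms Section 10.1.7 treats as the main concern.

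Safety and tolerability is a secondary objective of a single-arm trial, so the absolute rate is the result, with no control arm observed over the same window. Missing late events can only lower a cumulative rate or leave it unchanged. A reader of one Grade 3-4 percentage would also not know that non-serious events were counted to day 30 and serious ones to day 90.

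**Working it through.** The plan gives no figure for late toxicity, so there is none to reproduce. The check sets the collection routes side by side and follows an event through them.

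**Routes for an event with new onset after the last dose**

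| Route | Section | Open until | What it admits |
|---|---|---|---|
| General adverse events | 11.2.1; calendar in 7 | day 30 | any grade, serious or not |
| Serious adverse events | 11.2.2.1; 6.3 | day 90 | events meeting a criterion in 11.1.2 |
| Events of clinical interest | 11.6 | no end stated | overdose without symptoms or abnormal laboratory results; AST or ALT at least 3 times ULN with bilirubin at least 2 times ULN and alkaline phosphatase below 2 times ULN |
| Monthly contact | 7, footnote 12 | day 180 | mood and behavior only |
| Follow-up of known related events | 11.2.1 | resolution, clinical insignificance or new therapy | events already recorded; adds no new onset |

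**Event A: Grade 3 immune-related endocrine event, managed as an outpatient, onset day 45.** The general route is closed (45 > 30). The serious route is open (45 ≤ 90), but the event enters only if it meets a seriousness criterion. Admission of more than 24 hours does not apply, which leaves mainly the important-medical-event criterion, a matter of judgement. It is not the hepatic pattern. If it is not judged serious, it is not recorded.

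**Event B: the same event, onset day 100.** The serious route is closed too (100 > 90). Even an event that met a seriousness criterion would fall outside the window.

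**Event C: hepatic event, onset day 45.** If it meets the Section 11.6 pattern it is reportable whether or not serious. The calendar has no laboratory tests in long-term follow-up, so after the safety visit detection depends on unscheduled testing.

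**Effect on the reported rate.** One missed patient with no earlier Grade 3-4 event lowers the rate by 1/N, where N is the number in the safety set.
- N = 44 (Section 12.3): 1/44 = 0.0227, about 2.3 percentage points.
- N = 16, if the trial stops after stage 1: 1/16 = 0.0625, about 6.3 points.

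These N assume that every patient counted received both drugs, as the safety set in Section 12.4 requires.

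**Scale, by assumption only.** Let q be the proportion of patients with such an unrecorded event. The documents do not give q. Expected number missed = 44q; chance of missing at least one = 1 − (1 − q)^44.

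| q (assumed) | Expected missed | Chance of at least one |
|---|---|---|
| 1% | 0.4 | 36% |
| 2% | 0.9 | 59% |
| 5% | 2.2 | 90% |
| 10% | 4.4 | 99% |

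**The case against.** The windows agree with one another. Day 30 for all events and day 90 for serious ones is a deliberate two-tier scheme, repeated consistently in Sections 5.5.1, 6.3, 7, 11.2.1 and 11.2.2.1. Section 6.1 says only that late events may occur and gives no frequency. A rate to day 30 is a legitimate quantity, and the safety analysis is descriptive, with no test attached. Several routes also narrow the gap: life-threatening events are serious by definition; the important-medical-event criterion is broad; Section 5.6 calls for intravenous steroids in several Grade 3-4 events, which could lead to an admission that qualifies; the hepatic event of clinical interest has no end date; and related events that began by day 30 are followed up.

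All of that stands, and it limits the point to new-onset events that are neither serious nor the hepatic pattern. It does not remove it: those events have no route, and the endpoint states no window that would tell a reader so.

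Three stronger readings are tempting but not supported:
- A reader might infer that 67% to 83% of late non-serious immune events are lost. That is 1 − 30/90 and 1 − 30/180, and needs the assumptions that several months means 3 to 6 and that onset is even. It also says nothing about error in the overall Grade 3-4 rate, since on-treatment events are recorded in full.
- A reader might cite the target engagement beyond 21 days in Section 1.4.3. That figure is shorter than the 30-day window and is offered there as a reason for the dosing interval.
- A reader might infer that the bias is greatest in patients who stop early. Nothing in the documents shows this.

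**Conclusion.** The point holds in its limited form. The stated period of risk (Section 6.1), the recording window (Section 11.2.1 and the calendar) and the unwindowed endpoint (Sections 2.2.2 and 12.2.2) do not fit together. A new Grade 3 immune-related event after day 30 that is neither serious nor the hepatic event of clinical interest goes unrecorded, and a single Grade 3-4 rate mixes two follow-up periods.

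The number missed cannot be derived. The 2.3 points per patient assumes 44 in the safety set and no earlier Grade 3-4 event in that patient. The table over q shows scale only and is not an estimate. The response endpoint, the sample size and the two-stage stopping rule do not depend on any of this. It is an inexpensive improvement to safety data that the sponsor should make.

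**What to change.** **Section 11.2.1 and the calendar.** Keep day 30 for adverse events in general. Add that new immune-related events of Grade 3 or higher (the Table 3 categories), serious or not, are recorded with onset date at least to day 90, to match the serious-event window. Ask about them also at the monthly contacts already required to day 180 (Section 7, footnote 12) and at the later scheduled follow-up contacts (Section 6.3). Flag any new anti-cancer therapy started before onset. The calendar has no column for the day-90 follow-up visit named in Section 6.3, so it needs an entry there.

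**Section 12.4.2.** State the time window of the Grade 3-4 endpoint. Report these events to day 30, to day 90 and over all follow-up, with and without events that began after new therapy. If the sponsor decides against wider collection, the minimum is to state that the rate counts non-serious events to day 30 and serious events to day 90.

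**Cost.** One question at contacts already planned and one eCRF line; no new visit or test, and no change to treatment, dosing or stopping. The downside is real but small. Later contacts may be by telephone and without laboratory tests, so late events will be detected unevenly, and attribution is harder once new therapy has begun. The flag identifies that confounding but does not remove it, so the figures beyond day 30 should be labelled accordingly.
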